This trial is conducted in compliance with the Good Clinical Practice (GCP) regulations. All investigators and clinical research coordinators are properly trained in Good Clinical Practices and the Protection of Human Subjects in Research. The Site Monitoring, Auditing and Review Team (SMART) is responsible for assessing and promoting compliance with Good Clinical Practices at participating sites throughout the trial. This training is conducted at study start-up by the CSP SMART team. During the start-up phase, SMART develops study specific GCP guidance and tools for the sites, and provides training in the use of these materials and in the principles of GCP both at the study organizational meeting and during subsequent site visits. Monitoring of sites participating in the trial is executed according to the VA Cooperative Studies Program Guidelines.

B. Summary of Monitoring and Auditing Plans

- Monitoring Visits
 - Initiation visits at each site soon after study start-up.
 - Additional monitoring visits may be conducted as deemed necessary by study leadership or SMART.
- Audits
 - Routine audits – independent site visits to one or more sites during the Pilot, and each year during the first three years of the full-scale trial (site selection as determined by SMART).

- For-Cause audits – an independent audit of any participating site as requested by study leadership or CSP Central Office. For-cause audits may be announced or unannounced.

XVIII. PUBLICATIONS

A. Publication Policy

According to the policy of the Cooperative Studies Program, outcome data will not be revealed to the Study Chair or participating site investigators until data collection is completed and the study database is locked. This policy safeguards against possible biases affecting the data collection.

All presentations and publications from this study will follow CSP policy as stated in the CSP Guidelines. The presentation or publication of any or all data collected by site investigators on participants of CSP #592 is under the direct control of the Executive Committee. No individual site investigator has the right to perform analyses, make interpretations, make public presentations, or seek publication of any or all of the data without the approval of the Executive Committee. This is true whether the publication or presentation is concerned with the results of the principal undertaking or is associated with the study in some other way.

The Executive Committee has the authority to establish one or more publication committees (usually comprised of subgroups of site investigators and some members of the Executive Committee) for the purpose of producing manuscripts for presentation and publication. A presentation or publication, formulated by the Executive Committee or its authorized representatives, should be circulated to all members of the Executive Committee for review, comments, and suggestions prior to submission of the manuscript to the presenting or publishing body.

All publications must give proper recognition to the Department of Veterans Affairs Cooperative Studies Program and should list or reference all principal and site investigators in the study. Any manuscript, abstract, or letter to the editor submitted for publication or presentation must be sent

to the CSP Director for approval prior to submission for publication. Primary manuscripts will also be presented to the members of the study's DMC for information purposes.

B. Planned Publications

An intended plan of the main publications is given below:

Table 20. Intended study publication plan	
Manuscript	Projected time of submission
Study design and baseline patient characteristics	6 months after enrollment is completed
Primary efficacy analysis	6-12 months after end of study
Secondary and exploratory outcomes, including safety outcomes	12-18 months after end of study
Effect of atrial fibrillation on the elderly –with or without ICD –with respect to shocks, survival, QoL, etc.	12-18 months after end of study
Density of ICD shocks and hospital admissions for HF, or deterioration of LV function (if follow-up echo data is available)	12-18 months after end of study
Comparison of survival curve: OMT versus ICD without shocks versus ICD with shocks	12-18 months after end of study
Pacing in ICD (33% versus 66% versus 100%) relating to HF or death	12-18 months after end of study
Analysis of race and survival across secondary end-points	12-18 months after end of study
Analysis of beta blocker and survival	12-18 months after end of study
Analysis of enrollment and participation	12-24 months after end of study

REFERENCES

1. Goldstein, S. The necessity of a uniform definition of sudden coronary death: witnessed death within 1 hour of the onset of acute symptoms. *Am. Heart J* **103**, 156–159 (1982).
2. Zipes, D. P. & Wellens, H. J. Sudden cardiac death. *Circulation* **98**, 2334–2351 (1998).

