In contrast to the putative under-utilization of ICD among qualified patients, is the circumstance of implantation into individuals not meeting the evidence-based criteria of ICD. One recent survey of a registry of 111,707 patients revealed 25,145 (22.5%) receiving non-evidenced-based ICD implants ⁵⁵. If implantations are taken into account that are performed as a result of over-diagnosis of conditions for which ICD therapy is warranted, the rate of inappropriate implantation may be even higher ⁵⁶. Of note, some implantations found in registries not meeting evidence-based guidelines were not necessarily "inappropriate," since some variables in the registry may not be accurate ⁵⁷.

C. Study Rationale: ICD Implantation Among the Elderly

1. ICD Prevention of SCD in Aged Patients

One of the interests of the clinical community with regard to ICD implantation is to better understand which patients groups will benefit and which will not ^{58,59}, especially since the benefit of ICD therapy to prevent SCD and reduce overall mortality appears to be different across some patient subgroups ^{20,29,30,34,60}. For heart failure patients, age is a particularly important consideration, as the proportion of patients dying due to sudden cardiac death decreases steadily with age ⁶¹. It is reasonable to expect that elderly patients with severe left ventricular dysfunction would not gain the same overall survival benefit from prophylactic ICD therapy as would younger patients because the survival benefit of ICD therapy is directly dependent on its effect on SCD –the only preventable outcome with ICDs– and not on overall mortality ⁶². On the other hand, there is evidence suggesting that a population with higher baseline all-cause mortality risk does not preclude it from receiving substantial benefit from ICD therapy ⁵³.

2. Age Demographics in Previous ICD Studies

The age ranges of patients receiving ICDs in major clinical trials over the past 15 to 20 years are summarized in Table 4 below. The mean and median age of study populations of these past trials range between 50 and 65 years of age.

Table 4. Statistics on age of patients receiving ICD in previously published clinical trials. *= mean \pm std; †= median: range; ‡= median: inter-quartile range.

Age in Years	Size of ICD Group	Study
62 \pm 9*	95	MADIT-I ³¹
64 \pm 9*	446	CABG-Patch ³²
65 \pm 11*	507	AVID ⁶³
58 \pm 11*	99	CASH ⁶⁴
63 \pm 10*	328	CIDS ⁶⁵
52 \pm 12*	50	CAT ³³
64 \pm 10*	742	MADIT-II ³⁴

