The primary hypothesis of CSP #592 is that implantation of an ICD plus optimal medical therapy will reduce all-cause mortality in patients ≥ 70 years of age versus OMT alone.

C. Secondary Objectives

1. Co-morbidity Burden

A secondary objective of this study is to ascertain whether age, co-morbidity burden, or age and burden together, are determinants in mortality outcomes in the OMT versus ICD + OMT group.

2. Quality of Life

An additional secondary objective of the study is to determine the effect of ICD implantation plus optimal medical therapy on QoL among elderly patients compared with optimal medical therapy without ICD.

D. Exploratory Analyses

1. Prevention of Sudden Cardiac Death

This study will also ascertain whether –irrespective of the effect of ICD on all-cause mortality– the ICD is effective in its designed mechanism of action, i.e. preventing sudden cardiac death.

2. Reduction in All-Cause Hospitalization

[figure not shown]
As an additional exploratory analysis, CSP #592 decreases the number of hospitalizations versus those with optimal medical therapy alone.

III. SUMMARY OF STUDY DESIGN

A. Overview

This aim of this study is to test the safety and efficacy of ICD therapy as a strategy for the primary prevention of sudden cardiac death (SCD) in elderly patients meeting the standard ICD implantation criteria. CSP #592 is a two-arm study, with participants randomizing either to 1) ICD therapy plus optimal medical therapy, or 2) optimal medical therapy alone. The primary hypothesis is that ICD therapy + optimal medical therapy reduces all-cause mortality compared to optimal medical therapy alone. The secondary objectives of the study are to examine the influence of co-morbidity burden on the effect of ICD therapy, and to establish the impact of ICD therapy on QoL, sudden cardiac death, and all-cause hospitalization. This study will operate in a two-stage format: a one-year Pilot to assess feasibility of recruitment, followed by a five-year study wherein the main study objectives will be accomplished. The Pilot study will operate at 6 sites; the study in its full scope will operate at 27 sites, pending outcome of the Pilot stage.

Figure 2: CSP #592, multi-site, prospective, randomized clinical trial comparing ICD therapy against optimal medical therapy (OMT).

B. Study Population and Rationale

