Because the VA Vital Status File will be searched for all deaths, loss-to-follow-up for the primary endpoint is considered to be very negligible and was therefore not accounted for in the sample size calculation. Based on a 15% annual event rate in the control arm and a hazard ratio of 0.75, and the other assumptions listed above, a sample size of 1,462 (565 total primary outcome events) will be needed in order to achieve 90% power with a 2-sided Type I error rate of 0.05.

Using the target sample size of 1,462, the following scenarios were considered as sensitivity analyses:

- If the recruitment rate is less than anticipated, the study will still maintain 80% power to detect a hazard ratio of 0.75 with 1,084 participants (422 events).
- If the control group annual event rate was 3% lower than anticipated (i.e. 12% annual mortality rate) the study would still maintain 81.0% power to detect a hazard ratio of 0.75.
- If the effect size is smaller than hypothesized, the study would still maintain 80% power to detect a hazard ratio of 0.78.

3. Power for Secondary Analyses

The secondary objectives for this trial are to test the treatment interactions by co-morbidity level, and to test the change from baseline in the Minnesota Living with Heart Failure score. Neither secondary analysis will require adjustment for type I error, i.e. no “multiple testing” corrections: adjustments for multiple comparisons are required in confirmatory whenever results from multiple tests have to be combined in one final conclusion and decision; in studies with a single primary endpoint, all other endpoints are considered subsidiary and their results can only have an exploratory rather than a confirmatory interpretation – multiplicity corrections are not required¹²⁴. A sample size of 1,462 participants will yield the following power for secondary endpoints:

- Assuming equal enrollment across high- and low-burden groups, this study will reach statistical significance for an increased in therapeutic effect by 50% in the low-burden group (Charlson <3) and decrease in efficacy of 50% in the high-burden group (Charlson ≥ 3). Assuming a pooled standard deviation of 5 for change from baseline in Minnesota Living with heart failure score, the study will have 80% power to detect a 0.73 difference between groups in mean change from baseline at 12 months.

B. Interim Monitoring and Analysis

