1.2.3 Secondary Objectives

1.2.3.1 Co-morbidity Burden

A secondary objective of this study is to ascertain whether age, co-morbidity burden, or age and burden together, are determinants in mortality outcomes in the OMT versus ICD + OMT group.

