The secondary objectives for this trial are to test the treatment interactions by comorbidity level, and to test the change from baseline in the Minnesota Living with Heart Failure score. Neither secondary analysis will require adjustment for type I error, i.e. no “multiple testing” corrections: adjustments for multiple comparisons are required in confirmatory whenever results from multiple tests have to be combined in one final conclusion and decision; in studies with a single primary endpoint, all other endpoints are considered subsidiary and their results can only have an exploratory rather than a confirmatory interpretation – multiplicity corrections are not required²⁴.

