2.2.5 Supportive Co-Variate-Adjusted Analysis

Adjustment for significant treatment imbalances in baseline covariates will not be done in the primary analysis because this approach can be biased^{30,31}. Instead, exploratory analyses examining the treatment effect will be conducted using a model adjusted for a predefined set of important clinical covariates known to moderate or mitigate outcomes. The model will include factors that are known to increase risk in ICD patients, such as age at randomization, number of previous myocardial infarctions (MI), and baseline left ventricular ejection fraction (LVEF).

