2.2.6.1 Treatment Interactions by Co-Morbidity

The primary analysis of the treatment interaction with co-morbidity will take the form of a time to event, and will be analyzed using the same methodology (log-rank test) described for the primary outcome at a 0.05 2-sided significance level. The treatment effect will be summarized as a hazard ratio with 95% confidence interval. A test of treatment interaction by Charlson score <3 versus ≥ 3 (alternative subgroups) will also be performed.

In the study, the original Charlson score is a continuous variable. It is known that dichotomizing a continuous outcome into low or high values leads to a loss of information^{32,33}. Therefore, to keep the statistical power of the analysis, the testing of interaction will also be conducted by treating Charlson score as a continuous measure, via the Cox model, cf. the log-rank test for dichotomous formulation. The results from the above two methods will be compared, and they should be similar. In addition, a forest plot and treatment effects will be examined for each type of co-morbidity.

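### A secondary objective names age, and age with co-morbidity, as determinants of mortality by arm, but the planned interaction tests cover co-morbidity only

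*Combined protocol and SAP*

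**What the plan says.** Protocol II.C.1 and SAP 1.2.3.1 state the objective in the same words: "whether age, co-morbidity burden, or age and burden together, are determinants in mortality outcomes", for OMT versus ICD + OMT. It has three parts: age, burden, and the two jointly.

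The analysis sections then provide the following for mortality.

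- **Protocol XV.C.3.a:** treatment interaction by Charlson <3 versus ≥3, by continuous Charlson, and for each type of co-morbidity. A parenthesis allows unnamed alternative subgroups.
- **SAP 2.2.6.1:** the same Charlson split, and "testing of interaction will also be conducted by treating Charlson score as a continuous measure". A forest plot and treatment effects by co-morbid condition follow.
- **SAP 2.2.3:** treatment by Charlson stratum in the Cox model.
- **Protocol XV.C.1 and SAP 2.2.5:** a supportive model adjusted for factors "such as age at randomization", number of previous infarctions and baseline ejection fraction.

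Elsewhere age is a grouping for shock events (SAP 2.2.8) and a factor in the consent-questionnaire analysis (SAP 2.2.7.4).

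Where the objectives are restated, age is missing. Protocol XV.A.3 has "The secondary objectives for this trial are to test the treatment interactions by co-morbidity level, and to test the change from baseline" in the quality-of-life score. SAP 2.1 has "The secondary objectives for this trial are to test the treatment interactions by comorbidity level". The Coordinating Center director's letter, the protocol's summary of objectives and Protocol III.A also speak of co-morbidity only.

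**The concern.** A covariate's main effect shows whether older participants die sooner. It does not show whether the difference between ICD + OMT and OMT changes with age, which needs a treatment-by-age term. The plan contains no such term, no age subgroup, no age cut-point and no joint age-and-Charlson model.

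The gap matters because the background case is largely about age. Protocol I.C.1 says that "the proportion of patients dying due to sudden cardiac death decreases steadily with age", and Protocol I.C.4 reports that implantation in VA patients peaks at about 67 years and then declines. As planned, the trial would report whether the effect differs by Charlson score but not whether it differs between, say, a 72-year-old and an 84-year-old. Any age cut examined later would be post hoc, although the documents list age as part of a secondary objective.

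**Working it through.** **1. Objective set against analysis, reading the objective as effect modification**

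| Part of the objective | Planned treatment-interaction analysis of mortality |
|---|---|
| Co-morbidity burden | Charlson <3 v ≥3, continuous Charlson, each condition |
| Age | None; main-effect covariate only |
| Age and burden together | None; the covariates listed for the adjusted model do not include Charlson |

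**2. The plan's own base figure.** Protocol XV.A.2 gives 1,462 participants and 565 deaths for 90% power at HR 0.75, two-sided 0.05. From the projected cumulative mortality, 731 × (0.420 + 0.341) = 556 deaths, 1.5% below 565. A two-state model with the stated 15% annual mortality, 2.5% annual drop-in, 1% first-year drop-out and 2 to 5 years of follow-up (pilot participants 5 years) gives 574 deaths and 90.7% power. So 565 deaths is a fair base. The documents give no figure for an age interaction.

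**3. The interaction that is planned.** Protocol XV.A.3 takes the treatment effect as 50% larger in one Charlson group and 50% smaller in the other, with equal enrollment. Taking this as HR 1 − 0.25 × 1.5 = 0.625 and 1 − 0.25 × 0.5 = 0.875, with 282.5 deaths in each group:

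- SE = √(4/282.5 + 4/282.5) = 0.168
- z = |ln(0.625/0.875)| / 0.168 = 0.336/0.168 = 2.00, p = 0.046
- power about 52%

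**4. A continuous treatment-by-age term.** With 1:1 allocation and D deaths, SE per year = 2/(σ√D), where σ is the SD of age. The documents give no σ, so a range is shown. D = 565 and √565 = 23.77. The log ratio detectable with 80% power is (1.96 + 0.84) × SE.

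| Assumed σ (years) | SE per decade | Detectable log ratio | Detectable ratio of HRs per decade |
|---|---|---|---|
| 4 | 0.210 | 0.59 | about 1.8 |
| 5 | 20/(5 × 23.77) = 0.168 | 0.47 | about 1.6 |
| 7 | 0.120 | 0.34 | about 1.4 |

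A ratio of 1.6 would move the ICD hazard ratio from 0.75 to 0.75 × 1.6 = 1.20 over ten years of age.

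**5. Power at a smaller gradient.** Protocol Table 5 gives SCD-HeFT hazard ratios of 0.68 below and 0.86 above 65 years, a ratio of 0.86/0.68 = 1.26. Treating 1.26 as a per-decade gradient is an assumption, because the mean ages of the two groups are not given. At σ = 5, z = ln(1.26)/0.168 = 0.231/0.168 = 1.37, and power is about Φ(1.37 − 1.96) = 28%.

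**6. A three-way term.** For treatment by age by Charlson with four equal cells of 565/4 = 141.25 deaths, SE = √(4 × 4/141.25) = 0.337. The detectable ratio is exp(2.80 × 0.337), about 2.6. Power at a ratio of 0.625/0.875 = 0.714 is about 17%.

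**The case against.** *The objective may be prognostic.* Determinants of mortality outcomes can be read that way, and the adjusted model would then give an age coefficient. This stands as a limit: a reader might infer that the plan yields no age estimate of any kind, and the documents do not support that. But the objective is framed by the OMT versus ICD + OMT comparison, and the model is specified to examine the treatment effect. It cannot show whether that effect varies with age, and its listed covariates do not cover age and burden jointly.

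*Age may never have been intended.* The objective sits under a co-morbidity heading and most restatements omit age. Protocol III.G.3 explains why co-morbidity rather than age was chosen for stratification. This may well be one over-broad sentence carried into both documents, so deleting age is a legitimate repair. However, III.G.3 concerns randomization strata. It does not withdraw age from the objective, and an interaction test does not need stratified randomization.

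*The alternative subgroups could include age.* The phrase names no variable and qualifies the Charlson split. Other Charlson cut-points are the likelier meaning, and nothing about age is prespecified.

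*Earlier evidence shows no clear age gradient.* Protocol I.C.3 finds no consistent trend, and the cohort in I.C.5 has its lowest hazard ratio at ≥75 years (0.74, 0.76, 0.59). That leaves the question open but does not answer it.

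**Conclusion.** The mismatch holds. Under the effect-modification reading, two of the three parts of a stated secondary objective have no analysis, and the objective conflicts with its own restatements.

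Two stronger readings should be resisted. One is that the trial could answer the age question with useful precision. The figures do not show this: only a gradient of about 1.4 to 1.8 per decade is detectable with 80% power for an age SD of 7 down to 4 years, power is about 28% at 1.26 per decade with SD 5, and a three-way term is weaker still. The other is that the omission undermines the trial's main conclusion. Whether the ICD helps patients aged 70 or older is settled by eligibility and the primary analysis, and the plan treats all secondary results as exploratory.

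Low power is not a reason for silence, since the planned Charlson interaction has only about 52% power under its own scenario. It is a reason to estimate with confidence intervals. The mismatch itself rests on the text alone; the sizes rest on 565 deaths and the assumed age SD.

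**What to change.** In Protocol XV.C.3.a and SAP 2.2.6.1, add one exploratory Cox model with treatment, continuous age at randomization, continuous Charlson score, treatment × age and treatment × Charlson. Stratify it by Charlson <3 versus ≥3, and also by site if the stratification in Protocol XV.C.2 is kept. The stratification needs spelling out because SAP 2.2.3 uses Charlson only. Report the ICD hazard ratio with 95% CI at fixed ages, for example 70, 75, 80 and 85. Treat any treatment × age × Charlson term as descriptive only. Label the whole as estimation-focused and low-powered, under the existing policy of no multiplicity adjustment for secondary analyses.

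If no age analysis is intended, remove age from the objective in Protocol II.C.1 and SAP 1.2.3.1 so that the documents agree.

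The cost is some wording and one model. Age is already collected, and no participants or visits are added. The downside is one more exploratory test in the secondary family.
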